3.5.2. Step 1: Determining the Initial Target Sample Size

Although this is an adaptive clinical trial with sequential cohort design whereby the final sample size will ultimately be determined by the prespecified interim analyses, it was necessary for trial planning purposes to generate an estimated final sample size based purely on a priori assumptions.

Based on an average hospital cost of a patient hospitalized for \leq 72 hours with a primary diagnosis of HF (Diagnosis Related Group Code 291, 292 and 293) of \$8,600 (standard deviation: \$3,045), 68 patients (34 evaluable patients in each group) are required to have an 80% chance of detecting a decrease in hospital costs to \$6,500 at a significance level of 5%. The target sample size of the Furoscix cohort will initially be N=34 subjects.

Re-assessment of the sample size will be conducted once 34 subjects in the Furoscix cohort complete all study phases as per protocol (matched 1:1 to 4:1 to propensity matched controls to generate comparisons) by using a group sequential design and testing to allow for stopping. It is not expected that the sample size for the Furoscix Infusor arm would exceed N=75, but the maximum value cannot be definitively stated until the analysis at N=34 is completed.

3.5.3. Step 2: Produce Candidate Pool for Historical Cohort

EPI-Q will produce a candidate pool from which historical controls will be drawn via propensity match for comparison against the Furoscix Infusor cohort. This candidate pool will be comprised of HF-patient lives contained in the Marketscan Commercial Claims and Encounters (CCAE) and Medicare Supplemental Database. This pool will contain HF patients who will be characterized by binary indicators consistent with the demographic and background clinical variables (except laboratory tests) that are collected for the Furoscix Infusor arm (Appendix B).

Initially, the historical cohort will be created using the Marketscan Commercial Claims and Encounters (CCAE) and Medicare Supplemental Database for the years 2015-2017. The historical cohort will be later updated post acquisition of latest data up to year 2019.

The following inclusion criteria will be applied to identify patients with worsening HF:

1. Inpatient claims coded with an HF (ICD-9/ICD-10) diagnosis codes in primary position on the claim
2. Worsening HF defined by all admissions coded with a diagnosis-related group (DRG) for HF (291, 292, or 293)
3. Length of Stay 1-3 days
4. Service Category included ED Visit
5. Age 18-80 years
6. Continuous enrollment for 1 year before and 3 months after the index date
7. Background therapy including oral furosemide equivalents daily (Torsemide or Bumetanide)

First qualifying claim, where all the eligibility criteria is met, will be defined as the index date. Patients will be excluded if one of the following exclusion criteria is met:

1. Presence of diagnosis code for a complicating condition, other than HF (e.g. MI, pneumonia) as identified from the prospective arm data before final matching
2. Presence of diagnosis or procedure code for acute renal failure or Dialysis
3. Estimated Creatinine Clearance (CrCl) <30 (indicated by presence of diagnosis code for chronic kidney disease stage 4/5, ESRD or renal failure).

For the patients that meet all the eligibility criteria, the following demographic and baseline characteristics (i.e., candidate variables for propensity score calculation) will be determined and reconciled between the prospective study and historical controls' databases (i.e., only variables that can be consistently defined will be analyzed):

- Integer age
- Sex
- Geographic region (Northeast, North Central, South, West, Unknown)
- Concomitant Medication Use in prior 3 months (90 days) of index or enrolment date (inclusive)
 - Oral Diuretic
 - Digoxin
 - ACE Inhibitors
 - Nitrates and hydralazine
 - Oral anticoagulant
 - Statin
 - Platelet Inhibitor
 - Beta Blockers
- Baseline conditions/co-morbidities in prior year (364 days) of index or enrolment date (inclusive)
 - Myocardial Infarction
 - Hypertension
 - Diabetes
 - Hyperlipidemia
 - Peripheral vascular disease
 - Arrhythmias
 - Malignancy
 - COPD
 - Stroke
 - Valvular heart disease
 - PCI
 - Acute Coronary syndrome
 - Chronic Kidney Disease Stage

- Baseline resource utilization (All-cause and HF-related) in the 6 months prior to index or enrolment date
 - Hospitalizations
 - ED Visits
 - Clinic Visits

Once the data have been reconciled, distributions of the candidate variables will be assessed. Variables will be excluded from the analysis if none of the subjects from the prospective arm have the characteristic or there is little variability. To maximize the number of subjects from the prospective arm, when discrete variables have missing data, an “unknown” category will be created. With respect to missing data for continuous variables, the population mean will be imputed.

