	
Inclusion Criteria
 
1. Age 18-80 years2. NYHA Class II-III HF presenting to the ED for worsening HF at baseline3. On background therapy including 40-160 mg of oral furosemide equivalents daily (20-80 mg Torsemide or 1-4 mg Bumetanide)4. Signs of extracellular volume expansion, defined as one or more of the following:
a. jugular venous distentionb. pitting edema ($\geq 1+$)c. abdominal distensiond. pulmonary congestion on chest x-raye. pulmonary rales5. After initial emergency department evaluation and treatment (i.e., at the time of the care transition decision*), candidates for parenteral diuresis outside of the hospital, defined as all the following:
a. Oxygen saturation $\geq 90\%$ on exertionb. Respiratory Rate < 24 breaths per minutec. Resting Heart Rate < 100 beats per minuted. Systolic Blood Pressure > 100 mmHg6. Adequate environment for at-home administration of Furoscix 
*Decision point when the patient leaves the emergency department.
 
Exclusion Criteria
 
A Subject is not eligible for inclusion if any of the following criteria apply:
 
1. Presence of a complicating condition, other than HF that requires immediate hospitalization or anticipated hospitalization in the next 30 days2. Evidence of acute renal failure as determined at the discretion of the investigator3. Known allergy to the active and inactive ingredients of the study medication or device adhesive4. Any local abdominal skin condition on the day of treatment i.e. sunburn, rash, eczema, etc.5. Currently participating in another interventional research study6. Women who are pregnant or who could become pregnant and are not willing to use an adequate form of contraception7. Estimated Creatinine Clearance < 30 mL per minute by Cockcroft-Gault equation $\text{CrCl (mL/min)} = \frac{(140 - \text{age}) \times \text{Lean Body Weight (kg)}}{\text{Serum Creatinine (mg/dL)} \times 72}$ (x 0.85 if female)8. If baseline creatinine value is available: an increase of ≥ 0.5 mg/dL in creatinine from baseline9. HF requiring immediate hospitalization

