4. SELECTION OF STUDY POPULATION

4.1. Inclusion Criteria

Male and female patients 18-80 years old with NYHA Class II-III HF presenting to the emergency department with evidence of fluid overload requiring parenteral diuresis in the judgment of the investigator, and who are receiving 40-160 mg of oral furosemide equivalents daily (20-80 mg Torsemide or 1-4 mg Bumetanide).

Subjects may be enrolled in the study only if all of the inclusion criteria and none of the exclusion criteria are met.

1. Age 18-80 years
2. NYHA Class II-III HF presenting to the ED with worsening HF at baseline
3. On background therapy includes those receiving 40-160 mg of oral furosemide equivalents daily (20-80 mg Torsemide or 1-4 mg Bumetanide).
4. Signs of extracellular volume expansion, defined as one or more of the following:
 - a. jugular venous distention
 - b. pitting edema ($\geq 1+$),
 - c. abdominal distension
 - d. pulmonary congestion on chest x-ray
 - e. pulmonary rales
5. After initial emergency department evaluation and treatment (i.e., at the time of the care transition decision*), candidates for parenteral diuresis outside of the hospital, defined as all the following:
 - a. Oxygen saturation $\geq 90\%$ on exertion
 - b. Respiratory Rate < 24 breaths per minute
 - c. Resting Heart Rate < 100 beats per minute
 - d. Systolic Blood Pressure > 100 mmHg
6. Adequate environment for at-home administration of Furoscix

*Decision point when the patient leaves the emergency department.

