3.5.5. Step 4: Interim and Final Analysis with Propensity Match

Interim analyses to determine whether efficacy or futility has been reached will be conducted in a prespecified manner at N=10 and N=34 in the evaluable population. Additional interim analyses may be conducted as needed. Note that the enrollment for the prospective arm will continue as the interim analysis is carried out up to N=34, at which point re-assessment of sample size will be conducted.

For the interim analyses, the comparators will be historical controls drawn from the aforementioned candidate pool using a 1:1 to 4:1 propensity score matched approach. The propensity score matching process will be conducted via a caliper-based mechanism that allows for an iterative matching approach that will maximize the efficiency of the match protocol using methods reported by Millar and Pasta 2010.

The primary final analysis will include a 1:1 to 4:1 propensity match using the identical algorithm produced in the last interim analysis. Additional final analyses will explore the impact of increasing the ratio of cases to controls up to a 1:10 match. Note that the aforementioned matching method will be applied so that no Furoscix subjects will be dropped from the analysis due to the lack of a suitable match or matches.

The propensity scores (1 for each case and control) will be generated with the SAS PROC LOGISTIC function to produce a multivariate logistic regression. The propensity score is the predicted probability of receiving the Furoscix Infusor treatment. Both automatic stepwise and manual variable selection will be evaluated.

Criteria for propensity score matching are listed below:

- In addition to requiring that the absolute difference between the treatment arm propensity score and the control patient's propensity score be no larger than 0.01, exact sex, the absolute difference in age could be no larger than 5 years, and time between time zero visits could be no more than 730 days (or 1095 days). These key measure requirements reduced the data set substantially to a data set of potential matches.

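### The historical control pool omits the 40-160 mg oral diuretic window that every subject must meet, and no matching variable carries dose

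*SAP*

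**What the plan says.** **Subjects.** Protocol 4.1, criterion 3, reads "On background therapy includes those receiving 40-160 mg of oral furosemide equivalents daily (20-80 mg Torsemide or 1-4 mg Bumetanide". The synopsis has the same limits: "On background therapy including 40-160 mg of oral furosemide equivalents daily (20-80 mg Torsemide or 1-4 mg Bumetanide". The window is binding: "Subjects may be enrolled in the study only if all of the inclusion criteria and none of the exclusion criteria are met".

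**Controls.** SAP 3.5.3, inclusion criterion 7, reads "Background therapy including oral furosemide equivalents daily (Torsemide or Bumetanide". No milligram range follows, and none of the three control exclusion criteria mentions diuretic dose.

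**Matching.** Pool patients are to be "characterized by binary indicators consistent with the demographic and background clinical variables (except laboratory tests". Diuretic therapy enters the candidate list as an item named Oral Diuretic, under "Concomitant Medication Use in prior 3 months (90 days) of index or enrolment date (inclusive". The SAP then thins the list: "Variables will be excluded from the analysis if none of the subjects from the prospective arm have the characteristic or there is little variability". Apart from the propensity caliper of 0.01, SAP 3.5.5 requires "exact sex, the absolute difference in age could be no larger than 5 years" and a limit on the time between time-zero visits.

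**Costing.** Under SAP 3.5.3.1, mean cost benchmarks per event come from the dataset created for matching. Each patient's 30-day cost is the sum of those benchmarks over the events observed.

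**The concern.** The control arm stands in for what would have happened to the enrolled subjects had they been admitted. That requires controls whom the trial could have enrolled, at least on the criteria that claims can represent. The SAP does carry several limits across: age 18-80, acute renal failure, and creatinine clearance below 30 through a coded proxy. Criterion 7 follows the protocol's diuretic criterion closely but leaves out its range, and the SAP gives no reason.

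Background diuretic dose may be related to how advanced the heart failure is, and so to readmissions and visits within 30 days. If patients outside the window use care differently after matching, the control mean shifts for a reason unrelated to Furoscix. The primary comparison is a difference in mean cost in a non-randomised design, so such a shift goes straight into the estimate.

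**Working it through.** **1. The plan's own figure.** Inputs from SAP 3.5.2 and 3.3.3: means $8,600 and $6,500, SD $3,045, two-sided 5%, power 80%.

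n per group = 2 x [3,045 x (1.960 + 0.842) / 2,100]^2 = 33.0, rounded up to 34. The t-test solution is 33.99, also 34.

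The stated 34 per group reproduces. It is used here only to fix the design difference of $2,100 as a yardstick. The fix does not change N.

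**2. Eligibility side by side.**

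| Item | Subjects (Protocol 4.1) | Controls (SAP 3.5.3) |
|---|---|---|
| Daily oral diuretic therapy | required | required |
| Lower limit | 40 mg furosemide equivalents | none |
| Upper limit | 160 mg furosemide equivalents | none |

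Two groups are therefore eligible as controls but not as subjects: those below 40 mg and those above 160 mg.

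**3. Does the match restore the window?**

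- The Oral Diuretic item has no dose attached.
- Every subject and every control must already be on a daily oral diuretic, so the item is nearly constant across the combined data. The SAP's little-variability rule allows it to be dropped.
- The caliper, sex, age and time-zero constraints do not involve dose.
- The balance checks in SAP 3.5.5 cover candidate propensity variables only. An imbalance in dose would not be seen.

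**4. How a mismatch would reach the endpoint.** Under SAP 3.5.3.1 a patient's cost is the sum over event types k of (number of events) x (benchmark b_k). An out-of-window control's own claims cost is not used directly, which leaves two routes.

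- *Event counts.* If a share f of matched controls is outside the window and has d_k more (or fewer) events of type k than in-window controls, the control mean shifts by f x sum(d_k x b_k).
- *Benchmarks.* If out-of-window patients are in the dataset that supplies the benchmarks and move b_k by e_k, the difference between arms moves by sum over k of e_k x (mean count in controls - mean count in subjects). The same benchmark applies to both arms, so this cancels only where mean counts agree. They will not agree for the index admission: every control has one, and subjects are treated outside the hospital.

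**5. Direction.** For the first route, let f_L and f_H be the shares below and above the window, and D_L and D_H their mean cost differences from in-window controls after matching. The shift is f_L x D_L + f_H x D_H. If low-dose patients cost less and high-dose patients more, the terms have opposite signs. The documents give none of the four quantities.

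**6. Scale, as illustration only.** Write the net shift as f x D and assume f from 10% to 40% and D from $1,000 to $2,000, in either direction. Neither range comes from the documents.

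- Low end: 0.10 x 1,000 = $100; 100 / 2,100 = 4.8% of the design difference.
- High end: 0.40 x 2,000 = $800; 800 / 2,100 = 38.1%.

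These results show how the shift scales. They do not estimate it.

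**The case against.** The strongest reply is that the match already handles severity by other means. SAP 3.5.3 lists as candidates all-cause and HF-related hospitalizations, ED visits and clinic visits in the prior six months, chronic kidney disease stage, a long list of other conditions, and seven further drug classes. The pool is limited to stays of 1-3 days and excludes acute renal failure, dialysis and advanced kidney disease. Dose would affect cost largely through severity and use of care, so these variables may remove part of its effect. This stands. A reader might infer that nothing in the match deals with the problem, but the documents support only the narrower statement that nothing in it carries dose.

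A reader might also infer that dose is one of the few severity markers left because vital signs and NYHA class cannot be had from claims. The documents do not say so. SAP 3.3.4 and 3.5.3 except laboratory values only. SAP 3.6.1 lists NYHA class and vital signs as additional to the propensity variables, without giving a reason.

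Third, the claims codebook and the case report form are attachments whose content is not in the text, and a dose rule could sit there. That is possible, but criterion 7 neither states such a rule nor refers to one.

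Fourth, matching on dose needs dose in both arms. Protocol 5.7 names drug and duration as the details to record, not dose. The Subject Diary in Protocol 6.2.2 asks for dose, but only on treatment days. This also stands and limits the fix.

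**Conclusion.** The mismatch in eligibility holds on the text: followed as written, the SAP admits controls whom the protocol would have excluded, and neither the match nor its balance checks would show it. This rests on the SAP body, on the assumption that the unseen attachments contain no dose rule.

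The effect on the primary result is unknown in size and in sign. It would act through event counts and through the benchmarks, after whatever the other matching variables remove. A reader might infer that the missing upper limit lets in sicker, costlier controls and so inflates the saving. The documents do not support that, because the missing lower limit lets in low-dose patients as well. Nor can a dollar bias be obtained by applying a percentage to $8,600: that figure is an average hospital cost, not the 30-day endpoint, and the arithmetic would bypass both the benchmark costing and the matching.

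The point is a cheap improvement to the comparability of the arms, best made before the final match. It is not a demonstrated bias.

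**What to change.** **Change.** In SAP 3.5.3, state criterion 7 with the protocol's own enrolment window of 40-160 mg oral furosemide equivalents daily. Derive daily dose from the last oral loop-diuretic fill in the 90 days before index:

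daily dose = strength x quantity / days supplied

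Convert with the equivalence already in the protocol's ranges: torsemide x 2 (40/20 = 160/80 = 2) and bumetanide x 40 (40/1 = 160/4 = 40). This assumes that the pharmacy claims used for the medication indicators carry strength, quantity and days supplied. Draw the cost benchmarks from the pool after the restriction.

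**If the fields are missing.** State in the SAP that dose could not be aligned, and add a sensitivity analysis. One form is to report how large f x D would have to be, in either direction, to change the primary conclusion.

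**Dose as a matching variable.** Add daily dose to the candidate propensity variables, and so to the balance checks, only if baseline dose is recorded for the prospective arm. Screening has to establish it for eligibility, but Protocol 5.7 does not list it among the details to record.

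**Cost.** Claims programming, a short SAP revision and, if dose is to be matched on, baseline dose data for each subject. The candidate pool becomes smaller. SAP 3.3.2 calls it large, but SAP 3.5.5 intends that no subject be dropped for want of a match, so the match yield should be checked after the restriction. Dose derived from fills will carry some error, and some patients near the limits will be misclassified.

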3. INVESTIGATIONAL PLAN

3.1. Overall Study Design and Plan

This adaptive clinical trial will include a prospective treatment arm (i.e., Furoscix administered via the Furoscix Infusor) administered outside the hospital that will be compared to a propensity-matched historical control arm consisting of patients admitted to the hospital for ≤ 72 hours (i.e., TAU). This healthcare cost data from the control arm will be generated from administrative claims data. Eligible patients for the Furoscix arm will be patients with worsening HF due to congestion who initially present to the emergency department and who are expected to require parenteral diuresis. The decision as to whether a patient will be enrolled in the study to receive Furoscix will be made collaboratively by an emergency medicine physician and a heart failure specialist or cardiologist.

The control arm will be populated with claims data for patients who presented to the emergency department for worsening HF and are admitted to the hospital for ≤ 72 hours for the treatment of HF. The filter will be further strengthened by analyzing diagnostic codes and resource utilization during their hospital stay to remove patients with renal failure or those that were in the hospital for other reasons. Furoscix-treated patients will be matched to

controls from an administrative claims database in ratios ranging from 1:1 to 4:1 using methods reported by Millar and Pasta 2010.¹ The simulations will be used to find the matching ratio at which the level of precision is optimized without biasing the variance of the outcome measure. Additional methodological details are described in the prespecified statistical analysis plan.

Patients presenting to the emergency department with worsening HF and meeting all study eligibility criteria may be consented and enrolled in the study to receive diuresis outside of the hospital setting with Furoscix.

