4.2. Exclusion Criteria

A Subject is not eligible for inclusion if any of the following criteria apply:

1. Presence of a complicating condition, other than HF that requires immediate hospitalization or anticipated hospitalization in the next 30 days

2. Evidence of acute renal failure as determined at the discretion of the investigator
3. Known allergy to the active and inactive ingredients of the study medication or device adhesive
4. Any local abdominal skin condition on the day of treatment i.e. sunburn, rash, eczema, etc.
5. Currently participating in another interventional research study
6. Women who are pregnant or who could become pregnant and are not willing to use an adequate form of contraception
7. Estimated Creatinine Clearance < 30 mL per minute by Cockcroft-Gault equation
$$\text{CrCl (mL/min)} = \frac{(140 - \text{age}) \times \text{Lean Body Weight (kg)}}{\text{Serum Creatinine (mg/dL)} \times 72}$$
8. If baseline creatinine value is available: an increase of ≥ 0.5 mg/dL in creatinine from baseline
9. HF requiring immediate hospitalization

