- A logistic regression model will be developed to estimate a propensity score for each subject. The model will include candidate variables (defined in Section 3.5.2 Step 2: Produce Candidate Pool for Historical Cohort). The dependent variable will be binary and indicate either prospective patient or historical control patient. Backwards stepwise selection will be implemented with alpha level of 0.1 or 0.20 to identify predictor variables of receiving Furoscix (prospective subject vs. historical control). The final model including candidate variables identified from backwards stepwise selection will be used to generate a predicated probability (propensity score of receiving Furoscix) for each subject.
- For treatment arm, the variables will be defined at time zero (enrollment/ED visit); for control patients, the variables will be defined at index as a possible match.
- Once final matches are identified, to assess balance in confounding variables between cases and controls, for each of the candidate variables included in the propensity score modeling, effect sizes (normalized difference between cases and controls) will be calculated based on the differences between the matched pairs. An effect size of <0.20 will be deemed acceptable.
- Control patients' data were weighted based on the number of controls within each matched treatment arm patient set. For instance, if a control patient was part of a set with 1 other control patient, each control patient in that set was weighted 0.50 (1 divided by the set count 2).
- In addition to the effect size evaluation, the baseline characteristics, i.e. all initial candidate variables for propensity model, between the two cohorts will be compared statistically and any variable difference with a p value of <0.1 will be identified.

Analyses, whether they be interim or final, will be conducted sequentially using the SEQTEST procedure in SAS, which has been specified elsewhere (SAS Institute, 2009). Briefly, The SEQTEST procedure performs interim and final

analyses by comparing test statistics with corresponding boundary values obtained with the SEQDESIGN procedure. If the information levels for the test statistics do not match the information levels obtained with the SEQDESIGN procedure, the SEQTEST procedure modifies the original boundary values to adjust for actual (observed) information levels.

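### The control-pool version of exclusion 1 has no locked code list or time window, does not mirror the protocol criterion, and names MI, which is also a matching covariate

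*SAP*

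**What the plan says.** Protocol 4.2, exclusion 1, keeps a patient out of the Furoscix arm for "Presence of a complicating condition, other than HF that requires immediate hospitalization or anticipated hospitalization in the next 30 days". Prior MI is not an exclusion in that arm.

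SAP 3.5.3 (Step 2) builds the candidate pool of controls from claims. Its first exclusion is "Presence of diagnosis code for a complicating condition, other than HF (e.g. MI, pneumonia) as identified from the prospective arm data before final matching".

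The same SAP section lists the candidate variables for the propensity score. Under "Baseline conditions/co-morbidities in prior year (364 days) of index or enrolment date (inclusive" the first item is "Myocardial Infarction". A rule for dropping variables follows: "Variables will be excluded from the analysis if none of the subjects from the prospective arm have the characteristic or there is little variability".

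Protocol 3.1 describes the control filter in its own terms: "The filter will be further strengthened by analyzing diagnostic codes and resource utilization during their hospital stay", the aim being to remove renal failure and patients admitted for something other than HF.

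SAP 3.5.5 sets prespecified comparative looks at N=10 and N=34 and allows more as needed. It matches within a propensity-score difference of 0.01, says that no Furoscix subject will be lost for want of a match, and runs the final match "using the identical algorithm produced in the last interim analysis". Its balance criterion is: "An effect size of <0.20 will be deemed acceptable". Protocol 5.6 states that the study is unblinded.

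**The concern.** With no randomization, comparability rests on how the control pool is cut and then matched. Matching cannot bring back patients already removed from the pool, so the pool rules should mirror the eligibility rules of the treated arm and should be fixed before results are seen. This exclusion does neither.

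A list taken from prospective-arm data up to the final match can be settled or changed by people who have seen the cost comparison. The reach is wider than the match: SAP 3.5.3.1 derives the unit-cost benchmarks for both arms from the dataset created for matching, so a change to the list can also move the prices.

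A rule triggered by the mere presence of a code may also remove controls for a history that Furoscix subjects are free to have. MI is the visible case, because the SAP names it both as a reason to exclude and as a covariate to balance.

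**Working it through.** **The plan's own figure.** SAP 3.5.2 gives 34 per group for a difference of $2,100 (8,600 − 6,500), SD $3,045, two-sided 5% and 80% power. The normal approximation gives 2 × (3,045 × (1.960 + 0.842) / 2,100)² = 33.0, rounded up to 34; the two-sample t-test gives 33.99, also 34. The figure reproduces, and this point does not alter it.

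**The two exclusions side by side.**

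| Feature | Protocol 4.2 (Furoscix arm) | SAP 3.5.3 (controls) |
|---|---|---|
| Trigger | Condition other than HF that needs admission | A diagnosis code for such a condition |
| Time anchor | At the ED decision | None stated |
| Expected admission within 30 days | Excludes | No counterpart or proxy |
| Source of the list | Investigator's judgement at screening | Prospective-arm data |
| When fixed | At enrolment | By the final match |

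**Timing.** The final match follows the last interim analysis, since it reuses the algorithm from it. The wording therefore permits the list to be settled after the looks at N=10 and N=34. The commitment to an identical algorithm is made for the match; nothing extends it to the codes that define the pool.

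**MI, if the exclusion reaches back over the baseline year.** Then no control has prior-year MI. Let k of N Furoscix subjects have it, p = k/N. With the usual pooled SD,

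d = p / √(p(1 − p)/2) = √(2k/(N − k)).

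- N=34: k=1 gives √(2/33) = 0.25; k=3 gives √(6/31) = 0.44; k=5 gives √(10/29) = 0.59.
- N=10: k=1 gives √(2/9) = 0.47.
- N=75: k=1 gives √(2/74) = 0.16; k=2 gives √(4/73) = 0.23.

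The SAP bases its effect size on differences within matched pairs without giving the denominator. If the SD of the 1:1 within-pair difference is used (divisor N), d = √(k/(N − k)): at N=34, k=1 gives √(1/33) = 0.17 and k=2 gives √(2/32) = 0.25. On that version it takes two subjects, not one, to pass 0.20. The documents give no MI prevalence, so every k here is an assumption.

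On this reading the model also has a problem. MI would be present only among treated subjects. If the term is kept, it separates the arms, and those subjects have no control within 0.01, although the SAP promises to drop none. If the term leaves the model, MI stays unbalanced. The rule for dropping variables looks at absence in the prospective arm or low variability; it does not expressly cover absence from all controls.

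**MI, if the exclusion covers only the index stay.** MI during that stay excludes and MI in the preceding year is matched. The only overlap is the index date, which the covariate window includes.

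**The 30-day clause.** Leaving expected non-HF admissions in the control pool tends to raise control all-cause cost and admissions. Removing any control with a complicating-condition code tends to lower them. The documents give no rates, so the two cannot be netted.

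**The case against.** The strongest reply is that Protocol 3.1 supplies the missing window: controls are filtered on codes from the hospital stay, so an MI eight months earlier does not exclude. A reader might infer from the SAP wording that prior MI is simply absent from the controls and that the plan contradicts itself. The documents do not support that; MI can be an index-stay exclusion and a prior-year covariate. What stands is that the SAP does not say so. Appendix A (the claims codebook) is named but its content is not shown; it may hold definitions, but the SAP body still ties the list to prospective data.

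A reader might also infer that prospective data cannot supply such a list, because enrolled subjects were screened to lack these conditions. That goes too far. Under Protocol 6.2.1 consent precedes eligibility review, 9.1.7 requires a CRF for everyone who consents, and 9.1.6 includes a screening log, so screen failures could supply it. The objection to an open list in an unblinded study is untouched.

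On the 30-day clause it is fair to say that expectation of admission is a judgement claims do not hold. A reader might go further and infer that the gap inflates the saving by some share of the $2,100 target. That does not follow: the net direction is unknown, and $2,100 sets boundaries for HF-related cost (SAP 3.5.4), which counts only claims with a primary HF diagnosis (SAP 3.5.3.1), so a planned non-HF admission adds nothing to it.

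Finally, the SAP's own balance checks (effect size, and p<0.1 flags) could reveal an MI imbalance. But no remedy is stated, and matching cannot repair it once the pool lacks such patients.

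**Conclusion.** The control exclusion does not mirror the protocol exclusion. As worded, its list can be settled after comparative results are known. That part rests on the text alone and should be corrected.

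The MI overlap is an unresolved ambiguity, not a proven contradiction. On the look-back reading, one subject with prior MI among 34 gives a standardized difference of about 0.25 with a pooled SD, against the SAP's 0.20. On the index-stay reading, the problem shrinks to a single overlapping date. The size therefore depends on the window, on the assumed count of MI subjects and on the SD used.

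The missing 30-day counterpart is a real difference in screening that cannot be fully removed with claims data. The documents support neither a direction nor an amount for its net effect.

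**What to change.** In SAP 3.5.3:

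1. Replace the clause that draws the conditions from the prospective arm with a fixed code list of acute non-HF conditions. Lock it before the next comparative look and apply it only to the index ED/inpatient claim. Put the list in Appendix A, or reconcile it with what is there.
2. State that MI before the index stay does not exclude a control and remains a matching covariate. End the comorbidity window before the index claim, and before the enrolment date for Furoscix subjects, so that exclusion and covariate no longer overlap.
3. Acknowledge that the 30-day clause has no claims counterpart. At most, prespecify a sensitivity analysis that omits planned non-HF admissions in both arms. Leave the overall-cost endpoint as it is: Protocol 6.1.1 defines it as all direct medical costs, and redefining it would change a primary endpoint and bring in different ascertainment in each arm.

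The cost is writing the code list, a few sentences of SAP text and one re-run of the claims extraction.
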